#### Medtronic

### 2. Glossary

Term	Definition
ADE	Adverse Device Effect
AE	Adverse Event
ASADE	Anticipated Serious Adverse Device Effect
CA	Competent Authority
CAPA	Corrective and Preventive Action
CCE	Colon Capsule Endoscopy
CIP	Clinical Investigation Plan
CRC	Colorectal Cancer
СТА	Clinical Trial Agreement
CV	Curriculum Vitae
DD	Device Deficiency
DoH	Declaration of Helsinki
DR	Data Recorder
eCRF	Electronic Case Report Form
EC	Ethics Committee
EU	European Union
FAP	Familial Adenomatous Polyposis
FD	Financial Disclosure
FDA	Food and Drug Administration
GCP	Good Clinical Practice
IC	Informed Consent
ICF	Informed Consent Form
ICH	International Conference of Harmonization

Version 4.0 Version Date: 16Jun2022 Page 8 of 75

	_				
	le	ᄮ			
- IV	ш		m	n	II C
- 4			. •	ш	

Term	Definition		
IFU	Instructions for Use		
MDD	Medical Device Directive		
MedDRA	Medical Dictionary for Regulatory Activities		
PMDA	Pharmaceuticals and Medical Devices Agency		
RA	Regulatory Authority		
SADE	Serious Adverse Device Effect		
SAE	Serious Adverse Event		
SAP	Statistical Analysis Plan		
SID	Subject Identification		
UM	User Manual		

Version 4.0 Version Date: 16Jun2022 Page 9 of 75

Medtronic

### 3. Synopsis

г			
Title	A prospective single-center pilot study evaluating the technical feasibility of mucosal staining during COLON2 Capsule Endoscopy (CCE) procedure in Colorectal Cancer (CRC) high risk population,		
	when using MB-MMX (SPICE study)		
Clinical Study Type	Prospective, single-arm, single-center, non-randomized pilot post-market study		
Product Name	PillCam™ COLON2 Capsule Endoscopy System		
Sponsor & the funding source	Given Imaging Ltd., an indirect wholly owned subsidiary of Medtronic plc. ("Medtronic") [name] [name], [contact]		
Investigation Purpose	To evaluate the technical feasibility of mucosal staining during CCE in CRC high risk population, when using MB-MMX as a contrast-enhancement technique.		
Product Status	PillCam™ COLON2 Capsule Endoscopy System- CE marked since 2009		
Primary Objective(s) and/or Endpoint(s)s	Primary objective:  To demonstrate an effective colonic polyp enhancement during CCE procedure, when using MB-MMX as a contrast- enhancement technique.  Primary endpoints:  The percent of colonic polyps which have a visible contrast to the healthy colonic mucosa during CCE, as indicated by an experienced reader, using the subjective reader questionnaire (For each polyp – was there a contrast between the polyp and the healthy mucosa? Yes/No), out of the examined polyps (Appendix D).  The interference level of detrimental effects on the visualization of the colonic mucosa during CCE, due to use of MB-MMX per colonic segment. Detrimental effect will be considered as any observation, such as an excessive blue dye deposit, dark and dim appearance of the tissue, interfering with tissue visualization and will be evaluated on a scale from 1 (no interference) to 5 (high interference) to evaluate the level of interference, using a subjective reader questionnaire (Appendix D).		

Version 4.0 Version Date: 16Jun2022 Page 10 of 75

Medtronic

Secondary Objective(s)	Secondary objective:				
and/or Endpoint(s)	To evaluate the safety of CCE procedure while using MB-MMX.				
	Secondary endpoint:				
	All AEs will be reported by number, type, relatedness				
	(device/procedure), seriousness, severity and duration. All AEs will				
	be captured, regardless of severity.				
Study Design	Single-center, prospective, non-randomized clinical trial designed to evaluate the technical feasibility during CCE procedure, when using MB-MMX as a contrast- enhancement technique of mucosal staining in CRC high risk population.  Subjects will undergo a bowel preparation (single dose, 4L PEG), including 200 mg Methylthioninium chloride, corresponding to eight 25 mg MB-MMX tablets. An experienced Gastroenterologist will read the CCE procedure and complete a subjective questionnaire, to				
	evaluate mucosal enhancement during a CCE procedure, when using MB-MMX as a contrast-enhancement technique.				
Sample Size	Up to 15 subjects will be enrolled in 1 site in Spain.				
Sample Size	This is a pilot study where sample size will not be calculated.				
Inclusion/Exclusion Criteria	Inclusion Criteria:				
	
 
Male or female adults ages 45-75 years
 
Subject is classified as being at high risk for CRC due to one (or more) of the following risk factors:         
 
A personal history of colorectal polyps
 
A first-degree family history of colorectal cancer
 
Family/personal inherited syndrome (Lynch syndrome, Familial adenomatous polyposis {FAP}, other inherited syndromes linked to colorectal cancer)
 
Subject with currently suspected or diagnosed rectal bleeding, including positive FIT or positive fecal DNA test
 
Subjects under surveillance for CRC (last OC≥1.5 years)
 
 
 
Subject is willing and able to participate in study procedures, understand and sign the informed consent
 
				
	Exclusion Criteria:  1. Subject has a previous history or suspicion of inflammatory bowel or Crohn's disease, ulcerative Colitis or indeterminant Colitis				

 Version 4.0
 Version Date: 16Jun2022
 Page 11 of 75
 Medtronic

- 2. Subject has congestive heart failure or recent myocardial infarction (<3month)
- 3. Subject with moderate/severe renal disease and/ or severe hepatic impairment
- 4. Subject has uncontrolled diabetes
- 5. Subject has a severe, life-threatening disease
- 6. Subject with known gastrointestinal motility disorders
- 7. Subject has known delayed gastric emptying
- 8. Subject has undergone surgery of the luminal gastrointestinal (GI) tract, from esophagus to the rectum, other than uncomplicated appendectomy or cholecystectomy.
- Subject with any current condition believed to have an increased risk of capsule retention such as suspected or known bowel obstruction or pseudo-obstruction, stricture, or fistula (symptoms such as severe abdominal pain with accompanying nausea or vomiting)
- 10. Subject with dysphagia, any swallowing disorder, or any major gastrointestinal motility disorder
- Subject has a history of inadequate bowel preparation for colon imaging with colonoscopy, CTC, CCE, or DCBE (selfreporting)
- 12. Subject with known or suspected constipation history as defined by the following: as needing the use of medication (prescription or OTC) for management of constipation, or fewer than 3 BM/week regardless of medication use
- 13. Subject with a cardiac pacemaker or other implanted electromedical device
- 14. Subject with planned MRI examination within 7 days after ingestion of the capsule
- 15. The subject is taking antidepressant medicine or a medicine for psychiatric illness, such as:
  - selective serotonin reuptake inhibitor (SSRI)- as fluoxetine, fluvoxamine, paroxetine, sertraline, citalopram, escitalopram and zimeldine; bupropion, venlafaxine, mirtazapine, clomipramine, buspirone
  - medicines classified as Monamine Oxidase
     Inhibitors (often used for treating depression).
- 16. Subject has glucose-6-phosphate dehydrogenase (G6PD) deficiency and/or allergic to peanut/soya

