#### 9.2. Subject Enrollment

Written ICF will be obtained from each subject prior to performing any screening assessments. Once ICF is obtained, subjects will be screened to ensure they meet all of eligibility criteria prior to study enrollment. A subject is considered enrolled in the study once the ICF is signed and it is determined that all eligibility criteria are met.

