#### 10.1. Schedule of Events & Data collection

The study assessment in table 1 indicates the observations/ assessments/ data collection to be conducted throughout the study period.

Table 1- Schedule of events and data collection:

	Screening/ Enrollment	Preparation	Procedure Visit	Follow Up Visit
↓ Procedure Visit ⇒	V1		V2	V3
Time Schedule (Days)	(-30)-(-3) 	(-3)-0 	0	7±2
Inform consent	Х			
Eligibility criteria	Х			
Demographic data	Χ			
Medical History	Х			
Concomitant medication	Χ		X	
Vital Signs and height/weight measurements	Х		Х	
Urine Pregnancy test (when applicable)	Х	X 		
Provide Preparation materials (including MB-MMX) and subject instructions form	Х			
Low Fiber Diet		X		
Bowel Preparation intake		Х		
MB-MMX intake		X 		
Bowel preparation and MB-MMX compliance verification			Х	
Prucalopride administration			Х	
CCE administration			X	
Device Deficiencies			X	Х
Study Deviations	Х	Х	X	Х
AEs collection		Х	Х	X
Study exit				Х

<sup>1 Screening/enrollment process may start 3-30 days prior to visit 2.

<sup>2Preparation starts 3 days prior to visit 2

<sup>3 Urine Pregnancy test must be performed at day (-1) prior to the bowel prep/MB-MMX intake (when applicable).

<sup>4MB-MMX is administrated at day (-1).

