## MDT20062 SPICE Clinical Investigation Plan Version 4.0 Version Date: 16Jun2022 Page 29 of 75 Medtronic

administration Schedule. Subjects will be allowed to drink clear liquids and eat upon clinical team instructions.

Following capsule ingestion and intake of the 2nd bowel preparation boost, the subjects might be dismissed to continue the procedure at home, upon physician decision. In such case, the data recorder and sensor belt will be removed according to the clinical team instructions and up to 12 hours from ingestion.

Prior to discharge, the subject will be instructed to contact the study physician/ team in any case of an adverse event. In case a subject didn't excrete the capsule during the CCE procedure, he/she will be instructed to attempt to verify that the capsule exited the body and to inform the study team on the exit time, if possible.

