#### 10.5. Phone Call Follow-up Visit (visit 3)

5 to 9 days after the CCE procedure (after visit 2), each subject will be contacted by the study team over the phone, to verify that there have been no changes in their well-being following the procedure. In addition, capsule excretion will be verified.

An acceptable indication for safe excretion of the PillCam™ is capsule entry to the colon as visualized in the CCE video. The risk for retention may be considered null when the capsule enters the colon.

Subjects who didn't report capsule excretion until the phone call follow up visit, and the capsule didn't reach the Colon during the CCE procedure, as observed in the CCE video, will be evaluated for a need to perform abdominal x-ray to verify capsule exit, based on the investigator's judgment.

Should a subject miss a visit or the visit fall outside the pre-specified window of 5-9 days following the CE procedure, a study deviation must be reported. A subject will be considered as lost to follow-up if at least three attempts to contact the subject are unsuccessful. The method of attempt will be documented in subject's records.

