## MDT20062 SPICE Clinical Investigation Plan Version 4.0 Version Date: 16Jun2022 Page 34 of 75 Medtronic

#### 10.15. Subject Exit, Withdrawal or Discontinuation

A study exit eCRF is required for all subjects. The reason for study exit, including screen failure, will be documented on the applicable eCRF and in the subject file. The Sponsor must be informed of each withdrawal case. Prior to exiting a subject from the study, it is recommended to follow the subject until all ongoing device and/or procedure related AEs are resolved or unresolved with no further actions planned. At the completion of the follow-up visit, the subject will be exited from the study. A follow-up eCRF and a Study Exit eCRF will to be completed. Upon exiting from the study, no further study data will be collected, or study visits will occur for the subject, unless the subject has been referred to a colonoscopy procedure post the CCE procedure (de-identified colonoscopy report and images/videos may be collected) and/or AE follow up is required.

Subjects will be informed that they have the right to withdraw from the study at any time, without prejudice to their medical care, and are not obliged to state their reasons.

If the subject wishes to exit from the study (i.e. the subject revokes consent), the study site is required to document the reason for exit on the Exit eCRF. In addition, study site shall follow the regulations set forth by the governing EC. Per ISO14155 guidance, permission may be requested to follow up with the subject outside of the study, due to withdrawal based on issues related to the investigational feature safety or performance.

The investigator may withdraw a subject from the assigned study at any time if any of the following situations arise:

- 1. Subject did not provide consent/ withdrawal of informed consent by the subject
- The Principal Investigator deems that it is in the subject's best interest to withdraw from the study for subject's safety.
- 3. Subject's death
- 4. Occurrence of a Serious Adverse Device Effect (SADE), or severe side effects
- 5. Presence or appearance of any of the exclusion criteria/inclusion criteria not met
- 6. A significant CIP violation, as determined either by the sponsor or the investigator
- 7. Subject noncompliant with study procedures/visits

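### The MRI exclusion ends at day 7 and is applied only at screening, but capsule exit is first checked on schedule at the day 5 to 9 call

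*Protocol*

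**What the plan says.** Exclusion 14 has the same wording in the protocol synopsis and section 9.4: "Subject with planned MRI examination within 7 days after ingestion of the capsule". MRI is mentioned nowhere else in the protocol or SAP text available. It is absent from the risk sections (11.1, 11.2 and Table 2), the discharge instructions in 10.4 and the follow-up call in 10.5.

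**When the criterion is applied.** Section 9.2 states: "A subject is considered enrolled in the study once the ICF is signed and it is determined that all eligibility criteria are met". Table 1 in section 10.1 marks eligibility at visit 1 only, and its first note reads: "Screening/enrollment process may start 3-30 days prior to visit 2". Section 10.15 lets the investigator withdraw a subject for "Presence or appearance of any of the exclusion criteria/inclusion criteria not met".

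**When capsule exit is checked.** Section 10.5 schedules the contact: "5 to 9 days after the CCE procedure (after visit 2), each subject will be contacted by the study team over the phone". It adds: "In addition, capsule excretion will be verified". Before that, under 10.4, a subject who has not passed the capsule during the procedure is "instructed to attempt to verify that the capsule exited the body and to inform the study team on the exit time, if possible". Section 10.5 also accepts colon entry on the video as a sign of safe excretion, and continues: "The risk for retention may be considered null when the capsule enters the colon". Abdominal X-ray is available at the investigator's discretion (7.5, 10.5, 10.8).

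**The concern.** By including exclusion 14, the plan treats an MRI soon after ingestion as something to prevent. What would make an MRI acceptable again is that the capsule has left the body. The criterion uses a fixed count of days in its place, and it acts once, before ingestion.

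That leaves two openings. The bar stops at day 7 while the scheduled exit check can fall as late as day 9. And an MRI booked after screening meets no further scheduled question, whatever day it falls on. Either could put a subject in a scanner before anyone has established that the capsule is gone. What is at stake is the safety of an individual subject. The endpoints, analysis sets and estimates are untouched.

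**Working it through.** No sample-size or power figure is involved. The check compares time windows, counting ingestion as day 0 and reading the 7-day limit as including day 7.

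**Inputs**

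| Item | Days | Source |
|---|---|---|
| Eligibility decision | −30 to −3 | 10.1, Table 1 |
| Planned MRI barred | 0 to 7 | 9.4, no. 14 |
| Scheduled exit check (call) | 5 to 9 (7 ± 2) | 10.1, Table 1; 10.5 |

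**1. Call-window days outside the bar.** {5, 6, 7, 8, 9} minus {0, …, 7} = {8, 9}, so 2 of 5 days.

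**2. When a permitted MRI comes before the call.** A planned MRI on day *m* passes exclusion 14 if *m* ≥ 8. It falls on an earlier day than a call on day *c* if *m* < *c*.

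- *m* = 8: strictly before the call if *c* = 9 (1 of 5 permitted call days); on or before the call day if *c* = 8 or 9 (2 of 5).
- *m* = 9: never on an earlier day than a call made on time (0 of 5); on the same day, possibly earlier in it, if *c* = 9 (1 of 5). Otherwise the call must be late, missed or inconclusive.

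These are counts of permitted days, not probabilities. The plan does not say how calls are spread over the window.

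**3. Time between the screening decision and the end of the bar.** Shortest: 3 + 7 = 10 days. Longest: 30 + 7 = 37 days. Of this, the 3 to 30 days before ingestion could be covered by asking again at visit 2. The 7 days after ingestion can be covered only by an instruction to the subject. Table 1 does repeat another time-varying check, the pregnancy test, on day −1; it has no repeat for MRI.

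**4. Could exit be confirmed earlier by another route?**

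| Route | Section | Does it secure confirmation before an MRI? |
|---|---|---|
| Capsule passed during the procedure | 10.4 | Yes, for those subjects |
| Subject looks for exit and reports it | 10.4 | Only if possible; not required |
| Colon entry on video | 10.5 | Addresses retention; does not show the capsule has left the body |
| Abdominal X-ray | 7.5, 10.5, 10.8 | Discretionary; under 10.5 considered only if no exit was reported and the colon was not reached |
| Withdrawal if an exclusion appears | 10.15 | Discretionary; cannot help once the capsule is swallowed |

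A subject whose capsule reached the colon on video but who never saw it pass can finish the study with exit inferred, not observed. For that subject the gap can run beyond day 9.

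**The case against.** The strongest objection is that device warnings in this plan largely sit outside the protocol. The capsule is used under its approved instructions (7.1.1). Sections 7.6 and 11.1 refer to the user manual, the system manual and the risk file. Subjects receive an instructions form (10.3). None of these was available, nor were the consent pages, so a rule against MRI until exit may already exist. This stands as a limit: it cannot be said that subjects receive no warning. It does not remove the mismatch within the protocol, which should agree with those documents in either case.

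Other safeguards can be cited. Exclusion 18 covers contraindications to the device and exclusion 22 covers conditions that prevent compliance with device instructions. Both are screening criteria, and neither tells a subject what to do after ingestion. Subjects are asked at each visit about changes in their medical condition (10.12), which might bring a new scan to light but would not reliably catch a routine booking. The protocol's acceptance of colon entry as a sign of safe excretion is a reasonable rule for retention, but colon entry is only a surrogate for exit.

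It is also fair to say that 2 of 5 days overstates the calendar gap when calls are made on time, since the clear case is then an MRI on day 8 with a call on day 9. Finally, seven days matches the nominal call day and is easy to judge at screening. That is a good reason to keep the 7-day clause and add to it.

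**Conclusion.** The concern holds, as a minor participant-safety point. The protocol as written allows an MRI before capsule exit is confirmed in three situations: a planned MRI on day 8, an MRI arranged after screening, and an MRI on day 9 when the call is later that day, late, missed or inconclusive.

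Exposure is very small. It needs one of up to 15 subjects to have an MRI in this period with the capsule still inside. The boosts, prucalopride and suppository on day 0 (Appendix A), together with the motility, constipation and obstruction exclusions, make late passage unlikely. The documents give no figure from which to estimate how many subjects would be affected.

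The conclusion assumes that the 7-day limit includes day 7, and that the documents not available do not already close the gap. No endpoint, analysis set or estimate is affected.

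**What to change.** 1. **Discharge (10.4) and visit 3 call (10.5):** tell the subject to have no MRI until capsule excretion is confirmed, meaning seen during the procedure, reported by the subject, or shown by X-ray if an MRI is needed sooner.
2. **Exclusion 14 (synopsis and 9.4):** keep the 7-day clause and add a planned MRI that cannot be postponed until excretion is confirmed. This can still be judged at screening.
3. **Visit 2, before ingestion:** ask once whether an MRI has been arranged since screening.
4. Align all three with the user manual and the subject instructions form.

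The cost is one clause, one line in each of two sections, and one question. The downside is an occasional deferred MRI or enrolment, or an occasional abdominal X-ray (about 0.7 mSv by section 10.8) in a subject who needs an MRI and did not see the capsule pass. Sample size and analysis do not change.

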## MDT20062 SPICE Clinical Investigation Plan Version 4.0 Version Date: 16Jun2022 Page 12 of 75 Medtronic

	17. Subject consumes any of the medicinal products which		
	interacts with MB-MMX, as per MB-MMX label and		
	Investigator's discretion		
	18. Subject with allergies or known contraindication to the		
	device, medications or preparation agents used in the		
	procedure as described in the relevant instructions for		
	use/package inserts.		
	19. Subject use of opioid medication on a regular basis and		
	requires medication to treat opioid induced constipation		
	20. Subject currently participating in another gastrointestinal		
	clinical study (investigational drug or device) that might interfere with results of study		
	21. Females who are pregnant or breastfeeding at time of		
	bowel prep		
	22. Any condition which precludes compliance with study		
	and/or device instructions based on the clinical judgment		
	of the investigator		
	23. Subject who is considered to be part of a vulnerable		
	population (e.g. prisoners or those without sufficient		
	mental capacity)		
	24. Medtronic employees		
Study Procedures and	Day -30 to (-3)- Screening visit:		
Assessments	Obtain written informed consent		
	Confirm inclusion/exclusion		
	Medical history+ concomitant medication+ demographics		
	Vital signs		
	Urine Pregnancy test (when applicable)		
	Provide study bowel preparation martials & MB-MMX		
	tablets		
	Day (-3) - (-2) - low fiber diet		
	Day -1:		
	Clear liquid diet		
	
 
Urine Pregnancy test (when applicable)
 
		
	Bowel prep- 4L PEG+ MB-MMX (in accordance to the MB-		
	MMX IFU):		
	William Cy.		
	The first dose of 3 MB-MMX tablets should be		
	
 
The first dose of 3 MB-MMX tablets should be taken after drinking at least 1 L of PEG;
 
		
	The first dose of 3 MB-MMX tablets should be		

Version 4.0 Version Date: 16Jun2022 Page 13 of 75

Medtronic

	
 
The last dose of 2 MB-MMX tablets should be taken 1 hour after the second dose.
 
Day 0:         
 
Clear liquid diet
 
Vital signs
 
1 tablet of prucalopride 1mg
 
 
 
CE procedure, including boosts intake.
 

	Day 5-9: Follow-up phone call
Safety Assessments	Subjects will be asked at each visit, during the PillCam™ CCE procedure and during the follow-up phone call, about changes in their medical condition. All Adverse events and Device Deficiencies (DDs) will be recorded throughout the study period (starting at day -1 prior to the CCE procedure until the follow-up visit).
Statistics	This is a pilot study where no formal sample sizing will be calculated. Up to 15 patients are planned to be enrolled to this study.  Demographic and other characteristics will be provided.  Summary statistics (arithmetic mean, standard deviation, and range for quantitative variables) will be presented for the total study population. Frequency tables for qualitative data will be provided.  For the primary endpoint polyps contrast visibility, - the percent of polyps with visible contrast will be presented with 95%CI.  For the primary endpoint of determinantal effects evaluation, the level of interference will be presented as mean, standard deviation, median and range (scale of 1-5; 1 = no interference and 5 = high interference).  The percent of cases with at least one AE out of the total cases, will be presented with 95%CI.  Any deviation from specified statistical plan will be in addition to "per protocol" analysis and will be reported as such. Post-hoc analysis will be conducted according to the existing data gathered, if necessary.

Version 4.0 Version Date: 16Jun2022 Page 14 of 75

